### **1. Background**

Left Atrial Appendage (LAA) Closure (LAAC) is a potent technique of LAA isolation and exclusion for stroke prevention in patients with atrial fibrillation, with evidence from the PROTECT-AF and PREVAIL-AF trials, including their 5-year follow-up assessments, solidifying LAAC as a viable option in these patients with comparable stroke reduction in comparison to oral anticoagulation (OAC) as well as a reduction in bleeding risk, hemorrhagic CVA, and mortality [1-3]. However, the surge in the multiple methods of LAA exclusion has also brought to attention postprocedural complications specific to LAAC, namely, peri-device leaks (PDL) [4]. The stroke implication and classification of PDL itself still lacks consensus, with an increased thromboembolic (TE) potential due to PDL seen in patients with LARIAT and surgical ligation procedures, yet no statistically significant relationship seen in percutaneous and endocardial LAA closure approaches [5-9]. PDL > 5mm has been widely accepted as clinically significant, although there remains limited data with no current established guidelines. [5, 6, 10]. Placement of a septal occluder device such as Amplatzer Vascular Plug, Detachable embolization coils, Gore Cardioform Septal Occluder (CSO; W.L. Gore and Associates, Newark DE), and radiofrequency ablation (RFA) have all emerged as options to resolve residual PDL and post-surgical/ligation leaks [5, 10-12]. However, there exists no head-to-head comparison between these modalities. Given their emergence, we proposed a multi-center observational study to further assess and evaluate these three treatment modalities for their efficacy for leak closure, assessment of pre-, peri- and post-procedural characteristics after leak closure, TE events, and bleeding risk, and complication rates.

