## **2. Objectives:**

### Primary Objective:

Our main objective is to collect data from multiple different centers that use different modalities to currently treat either central or peri-device leaks that occur after incomplete LAA closure, and compare each modality in their efficacy and safety outcomes.

Primary Outcome: To compare the efficacy of the three current methods of PDL closure modalities in patients with prior incomplete LAAC.

Secondary Outcome: To compare the rates or reduction of rates of thromboembolic events and procedure-related complications in patients after successful PDL closure with any of the three closure modalities.

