## **Secondary Endpoints:**

1. To compare the reduction/rates of TE events and procedure-related complications (DRT, pericardial effusion/cardiac tamponade, or CVA/TIA) in patients after successful PDL closure with any of the three closure modalities
  - a. Periprocedural complications occurring from Postoperative day #0 – day 7
  - b. Delayed procedure-related complications and adverse events within 90 days of procedure

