## **Data/Variable Points for Collection:**

- Age
- Sex
- Height
- Weight
- BMI
- Diabetes (y/n)
- Smoking (y/n)
- Dyslipidemia (y/n)
- Prior stroke/TIA (y/n)

- Prior deep venous thrombosis/pulmonary embolism (y/n)
- Ejection Fraction
- History of CAD (y/n)
- Congestive heart failure (y/n)
- Chronic Kidney Disease (y/n)
- Type of Atrial Fibrillation (paroxysmal, persistent, permanent)
- Baseline antithrombotic regimen (aspirin, clopidogrel/prasugrel/ticagrelor, warfarin, direct oral anticoagulant, heparin)
- TIA/stroke after Watchman
- History of major bleeding
- High Fall risk (y/n)
- Previous major bleeding (y/n)
- Previous minor bleeding (y/n)
- Thromboembolism while on oral anticoagulant
- CHA2DS2-VASc Score
- HAS-BLED Score
- Time passed since LAA closure (months)
- Type of LAA Closure (watchman/watchman FLX, amulet, lariat, surgical ligation, atriclip)
- Device Size (if applicable)
- Thrombus on device (y/n)
- Peri-device/central leak size in mm
- Acute success (end of procedure closure) (y/n)
- Procedure duration (minutes)
- Flourosopy time (minutes)
- Contrast usage (mL)
- Hospital length of stay
- Type of procedural anesthesia (general vs light sedation vs local)
- Procedural imaging (TEE, ICE, or both)
- Devices attempted
- Devices deployed
- Combination procedures (combined AF ablation, or LAA occlusion + AF ablation)
- Size/number of devices (plugs/coils)
- Major procedural complications from postoperative day 0-7: stroke, TIA, air embolism, myocardial infarction, cardiac tamponade, device embolization, ventricular tachycardia
- Minor procedural complications from postoperative day 0-7: pericardial effusion
- Complications seen within 90 days of the procedure: cardiovascular death, non-cardiovascular death, stroke/TIA, pericarditis
- Follow-up transesophageal echocardiogram time (months)
- Size of leak at follow up (in mm)
- Follow-up time
- Follow up antithrombotic regimen

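### Bleeding risk is a stated aim in the Background, but no endpoint or post-closure data item captures bleeding, so no bleeding rate by modality can be derived

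*Combined protocol and SAP*

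**What the plan says.** Section 1 (Background) closes with the study's own purpose, a list of what the modalities will be evaluated for. It ends with "post-procedural characteristics after leak closure, TE events, and bleeding risk, and complication rates".

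The Primary Objective is to "compare each modality in their efficacy and safety outcomes", without saying which safety outcomes. Primary Endpoints concerns closure efficacy only. Secondary Endpoints covers thromboembolic events and "procedure-related complications (DRT, pericardial effusion/cardiac tamponade, or CVA/TIA", split into day 0-7 and within 90 days. Bleeding is not named in any of these places.

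Data/Variable Points for Collection has four bleeding-related items: "History of major bleeding", a yes/no item for previous major bleeding, a yes/no item for previous minor bleeding, and "HAS-BLED Score". After closure it has a major and a minor complication list for day 0-7, and a third list: "Complications seen within 90 days of the procedure: cardiovascular death, non-cardiovascular death, stroke/TIA, pericarditis". The Statistical Analysis section mentions no bleeding analysis.

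**The concern.** An aim needs an outcome variable. Here the only bleeding information describes the patient before leak closure. That can show whether the three groups started with similar bleeding risk, but not how much bleeding followed each modality.

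Bleeding could differ between modalities through the procedure itself or through the antithrombotic treatment that follows. The plan collects the antithrombotic regimen at baseline and at follow-up, and it collects stroke/TIA as an outcome. It therefore records the exposure and its thromboembolic side, but not its bleeding side. The Background also cites lower bleeding risk as a benefit of appendage closure over oral anticoagulation, so the outcome is not peripheral to the rationale. If bleeding did differ, the safety comparison could not show it, and a modality with more bleeding could look as safe as the others.

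**Working it through.** The plan gives no bleeding figure to reproduce, so the check is an item count from Data/Variable Points for Collection, set against the aims and endpoints.

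**Step 1. Bleeding-related items and their timing.**

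| Item | Type | Post-closure outcome? |
|---|---|---|
| History of major bleeding | history | no |
| Previous major bleeding | history | no |
| Previous minor bleeding | history | no |
| HAS-BLED | risk score among baseline variables; no follow-up score listed | no |

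That is 3 history items + 1 score = 4 items, of which 0 are post-closure outcomes. The two major-bleeding history items look like duplicates, and neither has a time window.

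**Step 2. Post-closure event types.**

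| List | Entries | Number | Named as bleeding |
|---|---|---|---|
| Major, day 0-7 | tamponade, device embolisation, air embolism, myocardial infarction, ventricular tachycardia, stroke, TIA | 7 | 0 |
| Minor, day 0-7 | pericardial effusion | 1 | 0 |
| Within 90 days | cardiovascular death, non-cardiovascular death, stroke/TIA (one entry), pericarditis | 4 | 0 |

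Total: 7 + 1 + 4 = 12 event types, of which 0 are bleeding events. There is also no access-site, transfusion or haemoglobin item. The remaining follow-up items (imaging time, leak size, follow-up time, antithrombotic regimen) are not bleeding outcomes.

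**Step 3. What happens to a post-closure bleed under these lists.**

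- A bleed presenting as tamponade or effusion by day 7, as a haemorrhagic stroke, or as a death is recorded, but under that label. No cause or haemorrhagic subtype is collected, so it cannot be counted as a bleed.
- A non-fatal access-site, gastrointestinal or other bleed has no entry in any list.

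The numerator of a bleeding rate is therefore unavailable in either window.

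**Step 4. Scale.** The documents give no bleeding rate. Assume, for illustration only, 2% to 6% major bleeding by 90 days. With the planned 160 patients:

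- 160 × 0.02 = 3.2 events
- 160 × 0.06 = 9.6 events

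If the three groups were equal in size (also an assumption, since no split is given), that is 3.2 / 3 ≈ 1.1 to 9.6 / 3 = 3.2 events per group. On these assumptions, counts by modality would be useful description but too few for a firm three-way test.

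**The case against.** The strongest reply is that no bleeding comparison was ever planned. Bleeding as something to evaluate appears once, in the Background. The objectives and endpoints, which govern the comparison, name efficacy, thromboembolic events and procedure-related complications. This stands, and it limits the point to a mismatch between a stated aim and the rest of the plan. It does not remove the mismatch, because the Background sentence is the study's own proposal and not a remark on the literature.

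Second, a reader might infer that the Background promises bleeding outcomes after leak closure. The sentence does not clearly say so: the words about leak closure attach to procedural characteristics, and bleeding risk is a separate list item. It could mean the risk profile that HAS-BLED and the history items describe. That reading is possible, but a baseline score describes case mix and cannot evaluate a modality. If it was intended, the aim should say so.

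Third, a reader might infer that every post-closure bleed is lost, or that any patient who bleeds would be entered as free of complications. The lists do not support this, because tamponade, effusion, stroke and death would capture some bleeds. What is lost is their identity as bleeds, together with the non-fatal bleeds that fit no entry.

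Finally, the broad reference to adverse events within 90 days under Secondary Endpoints might seem to cover bleeding. The data list reduces that window to four named event types, none of which is bleeding.

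**Conclusion.** The point holds as a gap between aim and data. Bleeding risk is a stated aim in the Background, 0 of the 12 listed post-closure event types is a bleeding event, and all four bleeding-related items are history or a score listed with the baseline variables. Followed as written, the plan cannot produce a post-closure bleeding rate by modality, and the safety comparison omits it.

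The conclusion rests on the text of the collection list and on no assumed rate; the 3.2 to 9.6 events above only show scale. The gap does not affect the primary endpoint. It should be corrected, because any statement on bleeding by modality after closure would otherwise have no data behind it.

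**What to change.** In Data/Variable Points for Collection, add major bleeding and minor/access-site bleeding (yes/no, with date and a stated definition) to the day 0-7 and within-90-day lists. In Secondary Endpoints, name bleeding as a safety component reported descriptively by modality, without relying on a three-way test.

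If the charts cannot supply post-closure bleeding, or abstraction is finished and will not be reopened, remove bleeding risk from the Background aim, or limit it to a description of baseline HAS-BLED, and make no bleeding comparison.

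The cost is two fields in each window and one endpoint line if abstraction is still open. The documents mix future and past tense, so this is unclear. If abstraction is complete, the cost rises to a return to source charts at each centre, with de-identified records to link back. Reported complication rates may become slightly less favourable. The wording-only alternative costs one edited sentence.

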## **2. Objectives:**

### Primary Objective:

Our main objective is to collect data from multiple different centers that use different modalities to currently treat either central or peri-device leaks that occur after incomplete LAA closure, and compare each modality in their efficacy and safety outcomes.

Primary Outcome: To compare the efficacy of the three current methods of PDL closure modalities in patients with prior incomplete LAAC.

Secondary Outcome: To compare the rates or reduction of rates of thromboembolic events and procedure-related complications in patients after successful PDL closure with any of the three closure modalities.

## **3. Research Methods and Statistical Considerations:**

### **Research Methods:**

This will be a multi- center retrospective observational comparison study.

### **Study Population:**

All patients at risk for stroke or thromboembolism that demonstrated any degree of the significant leak on follow up TEE imaging at least 4-6 weeks following either epicardial, endocardial, or surgical LAAC were included in this study population. All patients were evaluated and followed with imaging, and per investigators' respective clinical judgement, then proceeded to have an intervention for leak closure with either detachable embolization coils, vascular plugs/CSO, or RFA.

### Inclusion Criteria:

- patients at risk for stroke or thromboembolism that demonstrated any degree of the significant leak on follow up TEE imaging at least 4-6 weeks following either epicardial, endocardial, or surgical LAAC
- Patients undergoing any form of eccentric or centric/central leak closure with available modalities (detachable embolization coils, vascular plug/septal/ASD occluders, or RF Ablation). Criteria for this was made based on the judgement of the operator, with no specific cutoffs for leak size, follow-up time from LAAC to leak closure, etc)
- Age greater than 18 years

### Exclusion Criteria:

- Patients not undergoing leak closure after incomplete LAAC
- Patients unable to complete 45-day follow-up imaging for reevaluation of LAA leak
- Patients unable to consent

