## **Informed Consent:**

Given that this study was observational and retrospective in design, no informed consent was obtained or required. Patients who met inclusion/exclusion criteria were de-identified and added to word documents/excel spreadsheets.

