## **Statistical Analysis:**

Continuous variables will be summarized using mean and standard deviation, while categorical variables will be summarized as counts and percent of the total. Comparison analysis between groups will be made using Kruskal-Wallis tests for nonparametric data sets as appropriate. Leak sizes were measured initially and then via postprocedural follow-up, with overall rates of closure, minimal-mild leaks, and clinically significant leaks listed with associated p-values. All tests were two-tailed, and a  $P$  value less than 0.05 was considered statistically significant. All analyses were performed using SPSS Statistics version 28.0.0.0 (IBM).

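### Safety is compared only after successful leak closure, and the unanchored 45-day imaging exclusion may also keep early deaths out of the data

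*Combined protocol and SAP*

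**What the plan says.** All references are to the Combined protocol and SAP.

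- **Safety population.** The secondary outcome under Objectives and the first item under Secondary Endpoints both compare thromboembolic events and procedure-related complications "in patients after successful PDL closure with any of the three closure modalities". The main objective under Objectives names efficacy and safety for each modality, with no such restriction.
- **Success.** No section links successful closure to a criterion. Data/Variable Points for Collection has a yes/no item for acute success, judged at the end of the procedure. It also lists devices attempted and devices deployed. No complication item there is limited to successes.
- **Imaging exclusion.** Exclusion Criteria removes "Patients unable to complete 45-day follow-up imaging for reevaluation of LAA leak". No start point is given.
- **Entry to the dataset.** Under Informed Consent: "Patients who met inclusion/exclusion criteria were de-identified and added to word documents/excel spreadsheets". No section defines a safety set of all treated patients.
- **Safety windows.** Secondary Endpoints covers day 0 to day 7, and complications and adverse events within 90 days. The data list has "Major procedural complications from postoperative day 0-7: stroke, TIA, air embolism, myocardial infarction, cardiac tamponade" among its early items, and later "Complications seen within 90 days of the procedure: cardiovascular death, non-cardiovascular death, stroke/TIA, pericarditis".

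**The concern.** Both rules select patients for the safety comparison by something that happens after treatment starts.

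The success restriction is firm, because it stands in the text twice. A complication that ends an attempt without closure is a safety event of that modality, yet it lies outside the endpoint as written. If failures are more frequent in one modality, or complications cluster in failures, the comparison between modalities is distorted as well as the overall rate.

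The imaging exclusion is a conditional concern. If the 45 days run from leak closure, a patient must survive and be well enough to be scanned in order to enter the study. The day 0-7 window lies wholly before day 45, and 45/90 = half of the delayed window does too. A tamponade or stroke that is fatal before the scan would be lost both as a complication and as a death.

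**Working it through.** **1. What the 45 days run from.** The passages side by side:

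- For leak closure: the scan is for re-evaluating a leak, which presupposes one already found. Inclusion Criteria already requires a leak on TEE after LAAC and sets no limit on the time from LAAC to leak closure. Statistical Analysis says "Leak sizes were measured initially and then via postprocedural follow-up", and the data list records leak size at follow-up.
- For LAAC: the only imaging time with a stated start is the TEE at least 4-6 weeks (28-42 days) after LAAC, which is close to 45 days. Study Population says "All patients were evaluated and followed with imaging" and places the intervention after that.

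Leak closure is the likelier reading, but the text does not settle it. Under the LAAC reading, the early-death concern falls away.

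**2. What success means.** If it is the acute item, the endpoint drops attempts that failed on the table. If it is judged on follow-up imaging, a patient who dies before that imaging cannot be classed as a success, whatever the exclusion rule says. Either way the safety set depends on a treatment result.

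**3. Size.** The documents supply only the target of 160 and the 0-7, 45 and 90-day figures. The plan states no event rate to reproduce. Every rate and count below is an assumption.

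*Success restriction.* Let the complication rate be 5% in all attempts, success s = 0.90, and the rate in failures r. Rate among successes = (0.05 − (1 − s)·r)/s.

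| r | Calculation | Rate among successes |
|---|---|---|
| 0% | 0.050/0.90 | 5.6% |
| 5% | 0.045/0.90 | 5.0% |
| 10% | 0.040/0.90 | 4.4% |
| 20% | 0.030/0.90 | 3.3% |

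The restriction hides complications only if they cluster in failures.

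*Deaths before the scan (closure anchor, literal rule).* With 160 entered and k further treated patients who died before the scan, uncounted mortality = k/(160 + k). If all k fall in one modality of about 53 (160/3, equal split assumed), it is k/(53 + k).

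| k | Of all treated | Of one modality |
|---|---|---|
| 0 | 0% | 0% |
| 1 | 1/161 = 0.6% | 1/54 = 1.9% |
| 2 | 2/162 = 1.2% | 2/55 = 3.6% |
| 4 | 4/164 = 2.4% | 4/57 = 7.0% |

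*Non-fatal events (same condition).* Let the true rate be p = 5%, with imaging completed by q = 90% of patients without an event and by c of those with one. Observed rate = p·c/(p·c + (1 − p)·q), where (1 − p)·q = 0.855.

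| c | Calculation | Observed |
|---|---|---|
| 50% | 0.025/0.880 | 2.8% |
| 80% | 0.040/0.895 | 4.5% |
| 90% | 0.045/0.900 | 5.0% |
| 100% | 0.050/0.905 | 5.5% |

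The rate is understated only when c is below q. Closer follow-up after an event would push it the other way.

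**The case against.** A secondary endpoint may be narrower than a general objective. Inclusion Criteria governs eligibility and the data list governs collection, so neither contradicts a restricted endpoint. Failed attempts that were imaged are in the dataset and could be reported. Success also has an obvious candidate definition in the acute-success item. All of this stands: a reader might infer that the plan contradicts itself or leaves success with no possible meaning, and the text supports neither. What remains is that the stated comparison conditions safety on outcome, with an unlinked definition.

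On the imaging rule, being unable to complete imaging may have been meant for living patients, and listing death within 90 days suggests deaths were meant to be counted. Death is not among the complications named in Secondary Endpoints; it enters through adverse events within 90 days and the data list. The documents do not show how the rule was applied to deaths, so it cannot be said that early deaths were in fact excluded.

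Nor would zero recorded deaths before the scan show that deaths were hidden. Perhaps nobody died. The supported statement is that the rule would force a zero, so the zero carries no information.

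Finally, the ranges in the calculation include no bias and bias in the opposite direction, and the 7.0% needs four deaths all in one modality. They show sensitivity and do not demonstrate an effect.

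**Conclusion.** The concern holds in two parts of different strength. Firm: the safety comparison is stated only for successful closures, which is a post-treatment condition, narrower than the main objective and without a linked definition. Conditional on a leak-closure anchor and literal application: patients who die or are too ill before the scan would not be entered, so mortality up to the scan could not be assessed.

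The documents do not support a claim that complications are understated by a known amount, or that non-fatal rates are biased in a known direction. With a target of 160 across three modalities, even one or two missing deaths in one group could matter to the comparison. This should be fixed. Confidence is medium, because the anchor is unstated and all event rates are assumed.

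**What to change.** 1. In Objectives and Secondary Endpoints, replace the restriction to successful closure with *in all patients in whom PDL closure was attempted*. If results in successes are wanted, give them as a supplementary analysis defined by the acute-success item.
2. In Exclusion Criteria, state what the 45 days run from. If it is leak closure, apply the imaging condition only to outcomes that need imaging (leak closure and DRT). Count deaths and clinical complications from day 0 in all attempted closures.
3. Where excluded patients cannot be recovered, report by modality how many were excluded for missing imaging, with reasons including death, and state the resulting limit on the safety conclusion.

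**Cost.** The first change is nearly free for imaged patients, whose acute success and complications are already collected. The second needs some chart abstraction for unimaged attempts, which de-identification may limit or prevent. Safety rates may look less favourable, and imaging outcomes may have a smaller denominator than clinical ones.

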### **Primary Endpoints:**

1. To compare the efficacy of the three PDL closure modalities in patients with prior LAAC

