## **Sample Size:**

We will plan to aim for a total size of 160 patients in total among all three modalities.

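### Excluding treated patients without the 45-day scan conditions the efficacy comparison on a post-treatment event; this can bias it, in a direction the documents do not settle

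*Combined protocol and SAP*

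**What the plan says.** All references are to the combined protocol and SAP.

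- **Inclusion Criteria:** patients enter because they were treated: "Patients undergoing any form of eccentric or centric/central leak closure with available modalities".
- **Exclusion Criteria:** some of those treated patients are then removed: "Patients unable to complete 45-day follow-up imaging for reevaluation of LAA leak".
- **Primary Endpoints:** the only statement is "To compare the efficacy of the three PDL closure modalities in patients with prior LAAC". It gives no time point, denominator or definition of efficacy.
- **Statistical Analysis:** what will be reported is "Leak sizes were measured initially and then via postprocedural follow-up, with overall rates of closure, minimal-mild leaks, and clinically significant leaks listed with associated p-values".
- **Data/Variable Points for Collection:** the result at the end of the procedure ("Acute success (end of procedure closure) (y/n") and the later measurement ("Size of leak at follow up (in mm") are separate items. The list has devices attempted, devices deployed and combination procedures, but no item for a later repeat leak closure.
- **Research Methods:** the design is retrospective, so the exclusion is applied when treatment and scan status are already known.

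No section keeps all treated patients in the closure denominator, gives a rule for missing scans, reports exclusions by modality or plans a sensitivity analysis.

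**The concern.** Whether a patient completes the scan is settled after treatment and may depend on how treatment went. Making it a condition of study entry means the modalities are compared among patients selected on a post-treatment event. If re-scanning is related to outcome, each modality's closure rate is biased. If that relation, or the amount of missing imaging, differs between modalities, so is the primary comparison. The Inclusion Criteria leave the decision to treat to the operator, and the Objectives describe centres that use different modalities, so equal re-scanning cannot be taken for granted.

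Two groups show the problem most clearly. A patient recorded as not closed at the end of the procedure and never re-scanned disappears, although the plan collects that result. A patient who had a second closure before the scan would stay in, and the follow-up leak size would credit one modality with the effect of two procedures.

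**Working it through.** **Which scan is meant.** Inclusion already requires a leak on TEE at least 4-6 weeks after LAAC. A later re-evaluation of the leak is therefore most naturally the scan after leak closure, and the follow-up leak size item fits that reading.

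**Plan's own figure.** The Sample Size section says "We will plan to aim for a total size of 160 patients in total among all three modalities". No power, closure rate, allocation or dropout is given, so 160 cannot be reproduced. Nor is it stated whether 160 is counted before or after the imaging exclusion.

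**Direction.** Let *s* patients be scanned, *c* of them closed, and let *m* be treated but unscanned, with a share *f* of these being failures.

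- Reported rate: c / s
- Rate in all treated: (c + m(1 − f)) / (s + m)
- The first exceeds the second when c(s + m) > s·c + s·m(1 − f), that is, when f > 1 − c/s.

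Dropping unscanned patients therefore inflates the closure rate only if failures are more common among them than among the scanned.

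**Illustration for one arm.** Assumed inputs: 160/3 ≈ 53 patients (equal split), 43 truly closed, 10 not closed, 5 unscanned. The true rate is 43/53 = 81.1%.

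| Failures among the 5 unscanned | Closed / scanned | Reported rate | Difference from 81.1% (points) |
|---|---|---|---|
| 5 | 43/48 | 89.6% | +8.5 |
| 3 | 41/48 | 85.4% | +4.3 |
| 2 | 40/48 | 83.3% | +2.2 |
| 1 | 39/48 | 81.3% | +0.1 |
| 0 | 38/48 | 79.2% | −2.0 |

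Break-even is the arm's own failure share, 10/53 = 18.9%. One failure in five (20%) is almost exactly that.

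**Between modalities.** Suppose two modalities are equally effective and one has complete imaging. The spurious difference then runs from +8.5 to −2.0 points, depending on which five patients the other modality loses.

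**Same check on the whole study.** Assume 160 scanned, 128 closed (80.0%) and 16 further patients unscanned.

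- No failures among the 16: 144/176 = 81.8%, so the reported rate is 1.8 points too low.
- A quarter are failures: 140/176 = 79.5%, so 0.5 too high.
- Half are failures: 136/176 = 77.3%, so 2.7 too high.
- All are failures: 128/176 = 72.7%, so 7.3 too high.

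**What bounds would show.** Take the row with 40 of 48 closed. Worst case is 40/53 = 75.5% and best case is 45/53 = 84.9%. The width is 5/53 = 9.4 points. It depends only on the fraction unscanned and needs no assumption about why scans are missing.

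**The case against.** A reader might infer that the rule must inflate closure rates, because patients with a known failure have less reason to return. The documents do not support that. They say nothing about who is re-scanned or why. The opposite is equally arguable: a known residual leak is a reason to image, and a patient told the leak is closed may skip the scan. Unscanned acute successes are dropped too. A range built by removing only failures would show the extreme case and omit the null and negative results in the table above.

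A second objection is that an acute failure is not the study's efficacy result. Efficacy is undefined, and the Statistical Analysis section reports three follow-up categories. A yes/no result at the end of the procedure cannot be mapped to minimal-mild versus clinically significant leak, and it does not fix the state at follow-up. This stands. Counting unscanned acute failures as not closed is one defensible analysis and should not be the only one.

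Third, no section describes early re-treatment, so how often it occurs is unknown. Fourth, under Informed Consent, only patients who met the criteria were entered in the spreadsheets, so recovering the excluded patients is real work. Both are correct, and they bear on size and cost.

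None of these removes the central point: treated patients are excluded on a post-treatment event, and nothing in the plan shows how many, from which modality, or with what acute result.

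**Conclusion.** The point holds as a selection problem of unknown direction and size. Followed as written, the exclusion can bias each modality's closure rate and the primary comparison, so it is more than a missing detail. It rests on reading the 45-day imaging as the scan after leak closure, and on closure rates being taken from follow-up leak size.

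With the assumed arm of 53, a true rate of 81.1% and five unscanned, the error lies between −2.0 and +8.5 points. Arm size, closure rate and number unscanned are all assumptions, since the documents supply none of them. The claim that closure is overstated goes further than the documents allow: it would need the failure share among the unscanned to exceed 1 minus the closure rate among the scanned, about 19% in this illustration.

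**What to change.** 1. State that the imaging criterion refers to the scan after leak closure, and apply it only to the analysis of leak size in millimetres. Remove it as a study exclusion.
2. Base the closure rate on all patients with an attempted leak closure, by modality.
3. Report the number without the follow-up scan in each modality, split by acute result.
4. Give best-case and worst-case closure rates over all unscanned patients, acute successes and acute failures alike. Add one analysis that counts unscanned acute failures as not closed.
5. Add a data item for any repeat leak closure before the scan (yes/no, with date), and count such a patient as not closed for the first modality.

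The cost is a change of protocol wording, one data item and one sensitivity table. In addition, each centre must identify the treated patients now excluded and abstract their existing records. Reported closure rates may be lower or less precise. No patient's care changes.
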